9.6. Safety Oversight

9.6.1. Safety Review Committee (SRC)

The SRC will be composed of:

- PI, or designee
- Independent Safety Monitor (ISM)
- DMID Medical Monitor (MM) or designee;

The SRC will be responsible for reviewing halting criteria notifications in real time. If a halting rule is met, the SRC will meet for safety review and assessment to confirm the event. If any of the study halting criteria are confirmed, the SMC (section 9.6.2) will meet to evaluate the data and recommend appropriateness of further enrollments and/or vaccinations. The SRC will remain blinded as to treatment assignment.

9.6.2. Safety Monitoring Committee (SMC)

This clinical study will utilize an SMC, which is an independent group of experts that advises DMID. The primary responsibility of the SMC is to monitor subject safety. The SMC is external to DMID and comprises at least three voting members. The SMC will consist of members with appropriate Phase 1 study expertise to help interpret data from this trial. Its activities will be delineated in a SMC charter that will describe the membership, responsibilities, and scope and frequency of data reviews. The SMC will operate on a conflict-free basis independently of the study team. The DMID or SMC may convene *ad hoc* SMC meetings according to protocol criteria or if concerns arise during this trial.

The SMC will review the safety data at the following milestones:

- Organizational Meeting – conducted prior to the enrollment of study participants

- Scheduled Data Review Meetings – a preplanned, scheduled data review meeting – a scheduled meeting will take place to review cumulative data up to day 8 after dosing of the sentinel subject and recommend whether to proceed to enrollment of non-sentinel subjects
- Ad hoc meetings – an unplanned meeting convened for a specific safety concern – the committee will convene to review events that meet halting rules for sentinel and non-sentinel subjects
- Final Meeting – to review cumulative safety data (6 months following database lock)

All reviews by the SMC will be performed using blinded data initially (open session) and if necessary for safety of subject unblinded data will be reviewed in closed session. Vaccination data, including dose interruptions, modifications, and the associated reason(s), will be reported to the SMC.

9.6.3. Independent Safety Monitor (ISM)

An Independent Safety Monitor (ISM) will be assigned for the study site. An ISM is a physician with relevant expertise whose primary responsibility is to provide to DMID an independent safety assessment in a timely fashion. Participation is for the duration of the study and is a voluntary position that does not receive payment. The ISM must meet the requirements of the NIAID conflict of interest policy.

The ISM:

- Is in close proximity to the study site and has the authority and ability to readily access study participant records in real time.
- May be a member of the participating institution's staff but preferably be from a different organizational group within the institution.
- Should not be in a direct supervisory relationship with the investigator.
- Should have no direct involvement in the conduct of the study.

The ISM will:

- Sign a Conflict of Interest (COI) certification at the time they are asked to participate and provide updates to this information as needed.
- Receive reports of SAEs from the site PI and will be notified by email when DMID is notified of the SAE.
- Evaluate the SAE and report their clinical assessment to DMID, through DMID-CROMS SOCS in a timely manner and email the report to DMID-CROMS SOCS.
- Communicate with the investigator at the participating site as needed.

- Review additional safety related events at the request of DMID.
- Provide additional information to DMID and/or the SMC by teleconference as requested.

10. CLINICAL MONITORING

10.1. Site Monitoring Plan

Site monitoring is conducted to ensure that the human subjects' protections, study and laboratory procedures, and data collection processes are of high quality and meet sponsor requirements, ICH/GCP guidelines, and applicable regulations, and that this trial is conducted in accordance with the protocol, MOP, and applicable sponsor SOPs. The sponsor, DMID, or its designee will conduct site-monitoring visits as detailed in the clinical monitoring plan.

Site visits will be made at standard intervals as defined by DMID, and may be made more frequently as directed by DMID. Monitoring visits will include, but are not limited to, review of regulatory files, accountability records, eCRFs, ICFs, medical and laboratory reports, and protocol and GCP compliance. Site monitors will have access to the site, study personnel, and all study documentation according to the DMID-approved site monitoring plan. Study monitors will meet with the site PI to discuss any problems and actions to be taken, and will document site visit findings and discussions.

11. STATISTICAL CONSIDERATIONS

11.1. Study Hypotheses

There are two primary objectives for this trial: to assess the safety, tolerability, and reactogenicity of one dose of ChAd155-RG at 5×10^{10} vp per dose, or one or two doses of ChAd155-RG at 1×10^{11} vp per dose; and to compare the safety, tolerability, and reactogenicity of one or two doses of ChAd155-RG with three doses of RABAVERT. A secondary goal is to assess serum rabies VNA levels by a standard, WHO-approved, RFFIT, as assessed by immune response kinetics (through 12 months after the first dose of vaccination), seroconversion rates, and peak GMT. Also of interest are innate T cell and B cell responses, as well as ELISA binding antibodies. This trial, like other Phase I trials, is exploratory rather than confirmatory, and was not designed to test a formal null hypothesis.

11.2. Sample Size Considerations

This trial will enroll 50 subjects into four treatment arms: Group A (N=14) will receive one dose of ChAd155-RG at the lower dosage (5×10^{10} vp); Group B (N=14) will receive one dose of ChAd155-RG at the higher dosage (1×10^{11} vp); Group C (N=10) will receive two doses of ChAd155-RG at the higher dosage (1×10^{11} vp); and Group D (N=12) will receive three doses of RABAVERT. Randomization and safety, tolerability, and reactogenicity monitoring will be conducted as described in Section 5.3.1 and Section 9.6.1 respectively.

11.2.1 Adverse Events

The sample size of 10-14 subjects in each treatment arm is small given the early stage (Phase I) of the product's development; thus, the precision of estimates for AEs is limited. Rare AEs associated with dose level or number of doses are not demonstrable in a trial of this size; however, the probabilities of observing one or more AEs within a treatment arm given various true event rates are presented in Table 2. The minimum detectable event rates for various levels of power are displayed in Table 3.

Table 2: Probability of Observing an Adverse Event for Various Event Rates and Sample Sizes

N	"True" Event Rate	Probability of Observation (%)	N	"True" Event Rate	Probability of Observation (%)
8	0.1 %	0.8	12	0.1%	1.2
	0.5 %	3.9		0.5%	5.8
	1.0 %	7.7		1.0%	11.4
	2.0 %	14.9		2.0%	21.5
	3.0 %	21.6		3.0%	30.6
	4.0 %	27.9		4.0%	38.7
	5.0 %	33.7		5.0%	46.0
	10.0 %	57.0		10.0%	71.8
	20.0 %	83.2		20.0%	93.1
10	0.1%	1.0	14	0.1%	1.4
	0.5%	4.9		0.5%	6.8
	1.0%	9.6		1.0%	13.1
	2.0%	18.3		2.0%	24.6
	3.0%	26.3		3.0%	34.7
	4.0%	33.5		4.0%	43.5
	5.0%	40.1		5.0%	51.2
	10.0%	65.1		10.0%	77.1
	20.0%	89.3		20.0%	95.6

Table 3: Minimum Detectable Event Rates for Various Levels of Power and Sample Size

N	Desired Power Level	Detectable Event Rate (%)	N	Desired Power Level	Detectable Event Rate (%)
8	0.80	18.2	12	0.80	12.6
	0.90	25.0		0.90	17.5
	0.95	31.2		0.95	22.1
	0.99	43.8		0.99	31.9
10	0.80	14.9	14	0.80	10.9
	0.90	20.6		0.90	15.2
	0.95	25.9		0.95	19.3
	0.99	36.9		0.99	28.0

11.2.2 Immunogenicity

This trial was not designed to formally test any hypotheses associated with the immunogenicity data. The 95% confidence intervals for multiple observed seroconversion rates at various sample sizes were calculated assuming observed seroconversion rates of 90%, 95%, and 100%, as shown in Table 4.

Table 4: 95% Confidence Intervals for Seroconversion Rate for Various Rates and Sample Sizes

N	Seroconversion Rate	95% CI	N	Seroconversion Rate	95% CI
8	90%	(50 %, 100 %)	12	90%	(59 %, 100 %)
	95%	(56 %, 100 %)		95%	(66 %, 100 %)
	100%	(63 %, 100 %)		100%	(74 %, 100 %)
10	90%	(55 %, 100 %)	14	90%	(62 %, 99 %)
	95%	(62 %, 100 %)		95%	(69 %, 100 %)
	100%	(69 %, 100 %)		100%	(77 %, 100 %)

11.3. Planned Interim Analyses

For purposes of planning subsequent research and to allow internal and external presentations of data (e.g., national and/or international conferences and early publication of data), there will be one planned interim safety and immunogenicity analysis. Results of the interim analysis will not be used to make any decisions concerning the conduct of this trial.

Once at least half the subjects complete the Day 91 visit the clinical database will be cleaned, monitored, and a data freeze created. Unblinded analyses of safety, reactogenicity, and available immunogenicity data are planned. The interim report will be prepared by the SDCC after the interim clinical database is frozen and all VNA data through Day 91 for subjects for whom data are available at the time of database freeze are received.

Investigators will remain blinded to individual subject treatment assignment, and will be provided only data summaries aggregated by dose-group or blinded by-subject data.

For the purpose of advancing from the two groups of sentinel subjects to enrollment of the remainder of subjects, the SMC will review safety data. The halting rules described elsewhere in this protocol (Section 9.5) will be utilized to pause this trial if certain criteria are met.

11.3.1. Interim Safety Review

Safety data for the first set of four sentinel subjects will not be reviewed by the SMC before enrollment of the second set of four sentinel subjects if no pre-defined halting rule is met. Safety data for all 8 sentinels will be reviewed by the SMC prior to enrollment of the remaining 42 subjects. These sentinel reviews will not involve hypothesis testing and will not be considered in estimating the precision of any estimates made at the conclusion of this trial.

The interim analysis will include all safety and immunogenicity data through Day 91 for subjects for whom data are available at the time of database freeze. The interim safety analyses will be specified in the Statistical Analysis Plan and may include tables summarizing demographics, study status, and protocol adherence information. Tables and figures will present unsolicited adverse events by MedDRA System Organ Class (SOC) and Preferred Team (PT), severity, and relationship to study product. Solicited adverse events will be summarized by symptom, severity, and study day. Laboratory results will be summarized by parameter, severity, and study day. Blinded listings of early terminations, protocol deviations, and clinical data may be included. Since this early analysis of the data is not intended to impact the conduct of this trial, it has no impact on Type I error and adjustments are not planned.

11.3.2. Interim Immunogenicity Review

The interim analysis will include all available immunogenicity (VNA-RFFIT) data through Day 91 for the subjects for whom data are available at the time of database freeze, respectively addressing secondary objective. The interim immunogenicity analyses will include summaries of geometric mean titers (GMTs) and their associated 95% confidence intervals (CIs) as well as peak GMT by treatment arm at study timepoints outlined in Appendix A. Titer results will also be displayed in reverse cumulative distribution (RCD) curves by visit and treatment arm. No hypothesis tests or modeling will be included in the interim immunogenicity analysis. Since this early analysis of the data is not intended to impact the conduct of this trial, it has no impact on Type I error and adjustments are not planned.

11.4. Final Analysis Plan

The primary Clinical Study Report (CSR) will summarize all safety and protocol-specified humoral immunogenicity results, including all primary and secondary endpoint data, collected through the final study visit for the last subject. Prior to the interim database freeze, a formal Statistical Analysis Plan will be developed that specifies all planned analyses of primary and secondary endpoints, and indicates which analyses will be included in the interim analyses and primary CSR. In the following an abbreviated version of the planned primary and secondary analysis is provided. Additional exploratory humoral and cellular immunogenicity assessments may be summarized in one or more addenda to the main CSR.

11.4.1 Analysis Populations

Intent to Treat Population

The modified intent-to-treat (mITT) population includes all subjects who received at least one dose of study vaccine and contributed both pre- and at least one post-study vaccination venous blood samples for immunogenicity testing for which valid results were reported. For analyses using the mITT population, subjects will be grouped based on randomized treatment arm.

Per Protocol Population

The per protocol (PP) population includes all subjects in the mITT subset with the following exclusions:

- Data from all available visits for subjects found to be ineligible at baseline, according to the inclusion and exclusion criteria at the time of the subject's enrollment.
- Data from subjects who have a baseline rabies VNA concentration ≥ 0.5 IU/mL (for the immunogenicity analyses)

- Data from all visits subsequent to the following, such as:
 - Study withdrawal or treatment discontinuation,
 - Any study vaccination dose received out of window,
 - Receipt of non-study licensed live vaccine within 30 days before or after each study vaccination,
 - Receipt of non-study licensed inactivated vaccine within 14 days before or after each study vaccination,
 - Receipt of immunosuppressive therapy (e.g., corticosteroids) within 30 days before or after each study vaccination.
 - Receipt of chloroquine or hydroxychloroquine
- Data from any visit that occurs out of window, as defined in Appendix A “Window for each study visit”.

Safety Population

The Safety Population will consist of all subjects who have received at least one dose of vaccine and for whom any data on safety are available. Subjects will be classified according to the vaccine and dosage received. The primary safety analysis will be performed using this population.

11.4.2 Baseline Characteristics

Baseline characteristics overall and within each treatment arm will be summarized. For both continuous and categorical variables, appropriate summary statistics will be applied. For continuous variables, descriptive statistics will include the number of non-missing values, mean, standard deviation, median, minimum, and maximum. For categorical variables, descriptive statistics will include counts and percentages per category.

11.4.3 Safety Analysis Plan

Safety evaluations will be based on the incidence, severity and type of AEs. Clinically significant physical examination findings and vital signs will be documented on an AE case report form. Safety variables will be tabulated and presented for all subjects in the safety population, overall and for each treatment arm.

AEs will be coded by the Medical Dictionary for Regulatory Activities (MedDRA) for preferred term and SOC. The number and percentage of subjects experiencing each specific AE, along with 95% confidence intervals, will be tabulated by severity and by relatedness to vaccine. The number of AEs and SAEs will be reported by a detailed listing showing the type, MedDRA

coding, relevant dates (administration and AE), severity, relatedness, and outcome for each event.

Solicited local injection site and systemic reactogenicity will be summarized by severity for each day post vaccination (Days 1-7 post each vaccination) and as the maximum severity over all 7 days. Additionally, solicited AEs will be analyzed by taking the most severe response over the follow-up period, dichotomizing into a binary variable (none versus mild, moderate, or severe) and using exact confidence intervals to summarize the proportion of subjects reporting each symptom, any injection site symptom, and any systemic symptom. Solicited AEs will be summarized separately for each vaccination, and over all vaccinations by treatment arm.

Laboratory toxicities will be analyzed by taking the most severe response over the follow-up period, dichotomizing into a binary variable (none versus mild, moderate, or severe) and using exact confidence intervals to summarize the event and toxicity rates. Tabular and graphical summaries of events will be presented for each laboratory parameter, by type, severity (none, mild, moderate, severe), and time point post-administration.

Laboratory and vital sign data will also be presented as change from baseline. Variable transformations will be applied as appropriate. Shift tables may be produced for select laboratory parameters.

11.4.4 Immunology Analysis Plan

Seroconversion is defined as achieving a serum antibody level post-vaccination that is greater than 0.5 IU/mL, the pre-defined protective titer in the KSU RFFIT assay.

Seroconversion rates and GMT for rabies VNA titers will be calculated for each antibody timepoint by treatment arm, and will be summarized graphically.

Seroconversion rates and GMT will be presented with their corresponding 95% confidence interval estimates at each time point and overall peak GMT, and the pair-wise differences between seroconversion rates by treatment arm will be summarized by study day along with 95% confidence intervals. In an exploratory analysis, the relationship between the proportion of seroconverters and vaccine type, dosage, and number of doses may be examined using mixed-effects logistic regression models for longitudinal data.

All GMT calculations will use log10 transformed data, and the anti-log of the resulting point estimates will be reported for means and 95% confidence intervals. The relationship between the log-transformed titer values, vaccine type, and dosage, and dose number will be modeled using longitudinal regression methods in an exploratory analysis. The distribution of antibody titers will also be graphically summarized using the reverse cumulative frequency distribution of titers by study day, and treatment arm.

Cellular immunology assays and anti-vector antibody responses are exploratory endpoints and will be analyzed as described in the Statistical Analysis Plan (SAP).

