### **8.3. Exploratory Immunogenicity Analyses**

Summaries and analyses of immunogenicity data will be presented for the mITT population. If more than 5% of subjects, overall, would be excluded or have visits excluded from the PP population due to protocol deviations, then a PP analysis will also be performed.

The relationship between proportion of seroconverters and vaccine type, dosage, and number of doses may be examined using mixed-effects logistic regression models for longitudinal data. Also, the relationship between the log-transformed titer values, vaccine type, dosage, and dose number may be modeled using longitudinal regression methods in an exploratory analysis. Results will be summarized in [Table 25](#) and [Table 26](#).

The GMT of neutralizing antibody to the ChAd155 vector will be measured at Day 1 and one month after first vaccination (Day 29). The number of observations, GMT, and 95% CI for GMT will be reported in [Table 27](#) and [Table 28](#).

Analyses of CD4+ and CD8+ T cell and memory B cell data for the remaining exploratory endpoints will be outlined in an addendum to the SAP.

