**Table 24: Rabies VNA Pairwise Differences in Seroconversion Rates by Time Point - Per Protocol Population**

**Exploratory Immunology Analyses**

**Table 25: Rabies VNA Regression Analyses of GMT and Seroconversion Rate - Modified Intent to Treat Population**

**Table 26: Rabies VNA Regression Analyses of GMT and Seroconversion Rate - Per Protocol Population**

The format of these tables will be decided based on the results.

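### The exploratory VNA regressions enter vaccine type, dosage and dose number as separate terms, but with number of doses as an arm attribute the four regimens cannot yield a vaccine-type effect that compares regimens in the trial

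*Protocol*

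**What the plan says.** For titers, Protocol 11.4.4 commits to a model: "The relationship between the log-transformed titer values, vaccine type, and dosage, and dose number will be modeled using longitudinal regression methods". SAP 8.3 softens this: "the relationship between the log-transformed titer values, vaccine type, dosage, and dose number may be modeled using longitudinal regression methods". For seroconversion, SAP 8.3 has "The relationship between proportion of seroconverters and vaccine type, dosage, and number of doses may be examined using mixed-effects logistic regression models", and Protocol 11.4.4 names the same terms, also as optional. Both documents label the regressions exploratory.

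Neither document gives an equation, a coding, a reference level or a time term. SAP 8.3 sends the results to Tables 25 and 26, of which Appendix 1 says: "The format of these tables will be decided based on the results".

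The regimens are in Protocol 11.2: "Group A (N=14) will receive one dose of ChAd155-RG at the lower dosage"; "Group B (N=14) will receive one dose of ChAd155-RG at the higher dosage"; "Group C (N=10) will receive two doses of ChAd155-RG at the higher dosage"; and Group D (N=12) receives three doses of RABAVERT. Table 1 of the Protocol gives the RABAVERT dosage as 1 mL, with no viral-particle (vp) value. SAP 3.3 already defines vaccination group as a single four-level variable.

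**The concern.** Three explanatory terms need regimens in which they vary apart from each other. Here three doses occur only with RABAVERT, one or two doses occur only with ChAd155-RG, and the RABAVERT dosage is not on the vp scale. A reader of Table 25 would take a vaccine-type coefficient as RABAVERT against ChAd155-RG with dosage and number of doses held equal. The trial has no data at equal completed number of doses.

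The model also fills a gap. SAP 8.2 and 8.2.1 plan GMTs arm by arm, with no ratio between arms. The pairwise differences in SAP Table 23 concern seroconversion only and omit high dose x1 against high dose x2. The regression is thus the only specified between-regimen estimate on titers, and Protocol 3.1.3 lists a comparison of durability between the two vaccines as an exploratory objective.

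**Working it through.** The plan states no figure for this model, so there is none to reproduce.

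**Inputs.** Let A, B, C and D be the arm means of log10 VNA at one visit.

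| Arm | Type | Dosage | Doses | n |
|---|---|---|---|---|
| A | ChAd155-RG | low | 1 | 14 |
| B | ChAd155-RG | high | 1 | 14 |
| C | ChAd155-RG | high | 2 | 10 |
| D | RABAVERT | 1 mL | 3 | 12 |

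**Step 1: doses as an arm attribute, type not estimable.** Four arms support at most rank 4.

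- Doses categorical, dosage two-level: 5 columns, rank 4. The type column equals the three-dose column.
- Doses categorical, 1 mL as its own level: 6 columns, rank 4.
- Doses linear, 1 mL as its own level: 5 columns, rank 4. The type column equals the 1 mL column.

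**Step 2: doses linear, RABAVERT placed on the vp scale.** This gives 4 columns and rank 4. The fit is saturated, so linearity cannot be checked. The dose slope is C - B, and the type effect is D minus a projected three-dose ChAd155-RG mean:

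- coded high: D - [B + 2(C - B)] = D + B - 2C
- coded low: D - [A + 2(C - B)] = D - A + 2B - 2C
- coded 0 vp: D - 2A + 3B - 2C

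**Step 3: precision.** Variances are in units of the between-subject variance at one visit, assuming equal variance across arms and complete data.

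- Direct D - A or D - B: 1/12 + 1/14 = 0.155, SE 0.39
- Coded high: 1/12 + 1/14 + 4/10 = 0.555, SE 0.74, ratio about 1.9
- Coded low: 1/12 + 1/14 + 4/14 + 4/10 = 0.840, SE 0.92, ratio about 2.3

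**Step 4: sign.** The documents give no human GMTs, so these are assumed values in IU/mL.

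- A/B/C/D = 2/3/10/20. RABAVERT exceeds every ChAd155-RG arm (ratios 10, 6.7 and 2). The type ratio is 20 x 3/10² = 0.60 coded high, (20/2) x 3²/10² = 0.90 coded low, and (20/2²) x 3³/10² = 1.35 coded 0 vp.
- A/B/C/D = 4/6/4/3.5. RABAVERT is below every arm (0.88, 0.58 and 0.88). Coded high, the type ratio is 3.5 x 6/4² = 1.31.
- A/B/C/D = 2/4/4/8. D/B = 2.0, and coded high the type ratio is 8 x 4/4² = 2.0, so there is no reversal.

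Coded high, when D/B exceeds 1 the type ratio falls below 1 exactly when (C/B)² > D/B.

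**Step 5: dose number as active doses received so far.** Blood is drawn before the injection on vaccination days (Protocol 8.2.3). The counts at Days 8, 15, 22, 29, 91, 181 and 381 are: A and B, 1 throughout; C, 1, 1, 2, 2, 2, 2, 2; D, 1, 2, 2, 3, 3, 3, 3.

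- Categorical count, additive with visit: 11 columns, rank 11, so type is estimable. The three-dose term exists only in D from Day 29, so the weights on those D data in the type effect must sum to zero; in the calculation each is zero.
- Categorical count with type by visit: 17 columns, rank 16. Type is estimable at Days 8, 15 and 22, but not at Days 29, 91, 181 or 381.
- Linear count with type by visit: 16 columns, rank 16. Type is estimable at every visit, but from Day 29 on only by extending the one-to-two-dose slope to three doses.

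If dose number means injection number 1 to 4, placebo included, all arms share it and it is confounded with visit.

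**Step 6: vaccination group instead.** The arm matrix has 4 parameters and rank 4. The SEs are 0.39 for D - A, 0.39 for D - B and 0.43 for D - C (square root of 1/12 + 1/10).

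**The case against.** The strongest reply is that no model is written down, so separate fixed terms with doses as an arm attribute is an interpretation. That stands in part. It is the natural reading of number of doses in the logistic model. For titers, dose number could mean active doses so far, and then the type effect is estimable at early visits: Day 8 is a true one-dose comparison. So it would be wrong to infer that the effect must always be either non-estimable or an extrapolation.

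A reader might also infer that the regression will reverse the true difference between RABAVERT and ChAd155-RG. The documents do not support that. There are three arm differences, not one, and they can disagree in sign with each other. No human GMTs are given, and reversal turns on the unknown step from B to C and on the coding.

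The analysis is exploratory and optional in the SAP, no modeling enters the interim (SAP 6.6.2), and no formal immunogenicity hypothesis is tested. This bears on weight, not on correctness. The SAP also recognises that the two high-dose groups are the same before Day 22 (notes to Figures 2 and 4; Table 21), so its authors would probably not treat Group C as a two-dose arm at Days 8 and 15. The regression wording nevertheless leaves that open.

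Finally, the near-universal response described in Protocol 2.1 concerns recommended series of the licensed vaccines. It does not establish near-100% seroconversion after ChAd155-RG, so it is no documented ground for dropping the logistic model.

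**Conclusion.** The point holds for the listed terms. With number of doses as an arm attribute, the vaccine-type effect is not estimable, or it compares RABAVERT with an unobserved three-dose ChAd155-RG arm through a contrast set by an arbitrary coding. The 1.9-fold and 2.3-fold SE ratios belong to the high and low codings respectively and assume equal variances and full data. A change of sign against the observed arm differences is possible, not predicted. With a categorical count of active doses so far, the effect says nothing about completed regimens from Day 29 on unless type is assumed constant over time.

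The consequence is confined to exploratory Tables 25 and 26. It would be wrong to infer that the secondary immunogenicity results are compromised: by-arm GMTs, seroconversion rates and pairwise seroconversion differences do not use this model. The change is still worth making, because it costs almost nothing and supplies between-arm titer contrasts that the plan otherwise lacks.

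**What to change.** In Protocol 11.4.4 and SAP 8.3, replace the three terms with the four-level vaccination group of SAP 3.3, crossed with categorical visit, in a repeated-measures model for log10 VNA. Pre-specify these contrasts, reported as GMT ratios with 95% CIs:

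- B - A (dosage)
- C - B from Day 22 on (second dose)
- A - D, B - D and C - D (each ChAd155-RG regimen against RABAVERT)

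Align *will* and *may* between the two documents. Fixing the layout of Tables 25 and 26 in advance, and dropping the optional mixed logistic model in favour of the by-visit results already planned, would be tidy but are secondary; the point does not depend on them.

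The cost is a wording change in both documents and one model in place of another. No additional data are needed.
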